3.3 Study Groups

This is a double blinded study. Neither the participants nor the study team will know which group the participant has been assigned to. Records of the assignment will be kept with the pharmacist and can be accessed by the study team immediately in case of adverse events.

All study participants will undergo the same study procedures for screening and on the follow up visits. Women with symptomatic uterine fibroids planning to undergo surgery will be screened for participation.

Those found to be eligible will undergo pre-study evaluation during the screening period including:

- 1) Complete clinical evaluation.
- 2) Inclusion and exclusion criteria.
- 3) Uterine fibroid symptom and quality-of-life (UFS—QoL) questionnaires.
- 4) Fibroid number, location and size using ultrasound, and MRI if ultrasound is inconclusive.
- 5) Endometrial biopsy (if not done in the last 12 months).
- 6) Cervical smear (if not done in the last 12 months).
- 7) Lab: complete blood count, ferritin, liver enzymes, lipid panel.

We will use stratified block randomization with randomly permuted blocks of sizes 4 and 6 into one of the two arms. The randomization scheme will be stratified by race/ethnicity in three categories: African American, Caucasian, and Hispanic. All other races will be excluded (small numbers precludes proper stratification and analysis). The stratification will ensure similar distribution of race/ethnicity categories across the arms.

This is an “add-on” study, i.e. subjects in both arms will continue their current treatments for fibroids except hormonal birth control and medications contraindicated as per simvastatin prescribing information.

After 12 weeks of treatment, study participants will be re-evaluated, both clinically and by imaging. The results of the ultrasound will be discussed with the study subjects and they will be counselled about the need for the surgery if there are significant changes in fibroid size.

The fibroid tissue samples will be obtained for examination after the surgery (either myomectomy or hysterectomy). The fibroid tissue samples will be obtained for examination after the surgery (either myomectomy or hysterectomy). The study team will collect a 2.5 X 2.0 X 1.0 cm (or up to half of the tumor size) tissue sample from one fibroid for this study after the surgical pathology team has completed a preliminary evaluation of the delivered uterus.

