3.4 Study Duration

The participants will be enrolled in the study for a duration of 18-20 weeks. They will be visiting the study site 4 times for the study related visits and will be seen by the study team for follow up after their hysterectomy or myomectomy during their scheduled post-operative visits with their gynecologist. The first visit is the screening visit to obtain the informed consent and assess if the subject is eligible to participate in the study.

The study visits include:

1. Visit 1: Screening visit
2. Visit 2: Drug intake initiation visit at 0 weeks
3. Visit 3: 6 weeks after visit 2 during treatment period

4. Visit 4: 6 weeks after visit 3 during the treatment period

Follow up visits: Scheduled at subject's post-operative visits with their gynecologist for follow up.

The participant will receive the study medication at the treatment visits (Visit 2 and 3) for the next 6 weeks and study related assessments will be done at each of these visits. The study nurse will also remain in contact with the participant for the 12 week duration weekly to enhance compliance to study medication intake and to record adverse events if any.

The study nurse will also perform a drug reconciliation at each of the study visits to ensure that the patient is adherent to the study drug medication. The subjects will be instructed to bring all the medications that they forgot to intake or were left at the time of the research visit, these will be counted by the study nurse and a log of this information will be kept by the study research team. The regular weekly reminder calls from the study team will also complement the delivery of information about restricted food items such as grape fruit, cranberry juice for the intervals when the subject is not visiting the research team at Johns Hopkins Outpatient Clinic.

The subject undergoes hysterectomy or myomectomy at the end of treatment period (Visit 4) at week 12 and samples are obtained to study the fibroid tissue for molecular, cellular and histologic effects of simvastatin on human leiomyoma tissues. The study team will collect a 2.5 X 2.0 X 1.0 cm (or up to half of the tumor size) tissue sample from one fibroid for this study after the surgical pathology team has completed a preliminary evaluation of the delivered uterus. This tissue sample will undergo histopathological evaluation to study the effects of the study drug on fibroids.

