We do not anticipate having a participant in this study who will have an unexpected diagnosis of leiomyosarcoma. We will keep all tissue sections and samples until the final pathology report is made and are capable of returning tissue to the pathologist for evaluation, if necessary. Even when the patient has had a hysterectomy or myomectomy, the collected fibroid itself is not manipulated at the time of surgery, minimizing any untoward cell spillage into the peritoneal cavity. In the highly unlikely event that we do enroll a subject with the final pathological diagnosis of leiomyosarcoma we will treat this as a serious adverse event and report it immediately.

A double blinded, phase II, randomized controlled trial to study the effects of simvastatin in patients with uterine leiomyoma.

The subjects will be scheduled to undergo surgery within 1 week following the 12 weeks treatment period of the study.

Standard clinical care will be provided pre and post hysterectomy/ myomectomy to the participants independent of the study assessments. The study nurse will follow up with the study participants during their 2 and 6 weeks post-operative visits with the subject's gynecologist.

More detailed information about the study visits and study related procedures is shown in Figure 1 and Table 1 below.

Study Design: Flowchart of the study design can be seen in Figure 1 below.

A double blinded, phase II, randomized controlled trial to study the effects of simvastatin in patients with uterine leiomyoma.

[figure not shown]

Figure 1: Study design flowchart.

Table 1: Detailed Flowchart of Study Assessments

A double blinded, phase II, randomized controlled trial to study the effects of simvastatin in patients with uterine leiomyoma.

Visit	Visit 1	Visit 2	Visit 3	Visit 4	Follow up Visit
Activity	Screening	Beginning of the treatment period	6 weeks after start of treatment period	12 weeks after start of treatment period	Scheduled at 2 and 6 weeks post surgery
Informed Consent	X				
I/E criteria	X				
Demographics	X				
Smoking/Alcohol History	X				
Medical History	X				
Reproductive, menstrual, fibroid history	X				
Medication reconciliation & restricted food discussion	X	X	X	X	
Vital signs	X	X	X	X	
Physical examination	X			X	
Gynecological exam	X			X	
Cervical smear	X				
Ultrasound examination	X			X	
Endometrial biopsy	X				
Labs	X			X	
Inform about contraception	X	X	X	X	

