5. STUDY INTERVENTIONS

5.1 Interventions, Administration, Duration

5.1.1 **Intervention:** Simvastatin tablets and placebo tablets will be encapsulated prior to being dispensed to the subject from the investigational drug pharmacy and will look similar. The participant will receive the study medication for a duration of 6 weeks at a time. The dose of the simvastatin tablets is 40 mg/ day. More information of dosage is in the section for “Rationale for Dosage Regimen”. The subject will be advised to take the medicine in the evening at a fixed time every day. The placebo will consist of Starch 1500 packed into matching capsules.

A safety report will be generated and will include updated information such as adverse event monitoring, compliance rates, etc. about all the participants in the study.

5.1.2 **Administration:** The study drug will be taken orally by the participant for a total period of 12 weeks divided into intervals of 6 weeks each followed by study visits with the team. The participants will be advised to take the tablet orally at the same time every day, in the evening, with water.

5.1.3 **Duration:** The participants will take the study drug/ placebo for a duration of 6 weeks at a time (12 weeks in total). The prescriptions for the study drug/ placebo will be refilled at an interval of 6 weeks. The subject will be seen at the drug intake initiation week (Visit 2), after 6 weeks (Visit 3) and 12 weeks (Visit 4). After the last visit, the subject will undergo their scheduled hysterectomy/ myomectomy to collect fibroid samples.

After the hysterectomy / myomectomy, fibroid samples collected will be examined and stored for further evaluations.

Thus, the participant will effectively be a part of the study for a duration of 12 weeks prior to their hysterectomy/ myomectomy. The study team will follow up the subjects after their surgery at their 2 and 6 weeks post-surgery visits to monitor for any adverse events.

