The study medication will be dispensed through the Investigational Drug Pharmacy at Johns Hopkins. The subject will be informed about the medication intake. The study medication is an oral tablet to be taken once a day in the evening at the same time. The dose of the simvastatin group is 40 mg/ day.

The restricted foods such as grapefruit, cranberry juice, and dietary supplements will be discussed with the subject.

At one time the participant will be provided medication for 6 weeks. The study nurse will contact the participant every week at the participant’s preferred time to ensure compliance and monitor any adverse events that may occur after starting the intake of the medication.

Visit 3 and 4: At 6 and 12 weeks from Drug Initiation Visit

Visits 3, and 4 will be at 6 and 12 weeks after the initiation of the study drug. These will occur at Johns Hopkins outpatient clinic to follow up with the study participant at intervals throughout the study duration of 12 weeks.

There will be review of concomitant medications that the subject is taking and an adverse events assessment at each visit. The restricted foods such as grapefruit, cranberry juice, and dietary supplements will be discussed with the subject.

The study questionnaires will be filled at visit 4. The subject will be informed about the ultrasound result at 12 weeks, and counselled about the need for surgery if there are significant changes in fibroid size.

Follow up Visit

The participant will have their scheduled hysterectomy or myomectomy and the fibroid sample will be collected and evaluated for histologic effects of simvastatin on fibroids.

The standard clinical care follow up will be provided to the subject by their gynecologists.

The study team will follow up with the subjects after their surgery at their 2 and 6 weeks post-surgery visits to monitor for any adverse events. The subjects will fill the final questionnaires for the study at the 6 week post surgery visit.

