6.4 Blood sampling

15-20 mL blood will be obtained for CBC with differential, hemoglobin, hematocrit, ferritin, liver enzymes and lipid panel pre and post study duration to compare the results at baseline and end of study.

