8. CRITERIA FOR INTERVENTION DISCONTINUATION

Subjects will only receive the study drug simvastatin or placebo as a participant of the research study. Subjects may voluntarily withdraw from the study at any time and for any reason. The investigator may discontinue the subject's participation in the study if he believes it necessary for any reason including:

- 8.1 Intercurrent pregnancy
- 8.2 Symptom improvement where surgery is not necessary
- 8.3 Occurrence of an adverse event that precludes further participation in the study at the discretion of the investigator
- 8.4 Clinically significant adverse results in laboratory testing
- 8.5 Failure to comply with the protocol
- 8.6 Evidence of significant, persistent side effects

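### Section 8 lets the investigator end participation but writes no option to stop study drug and stay in follow-up, so a woman removed before Visit 4 leaves no scheduled post-baseline laboratory value or fibroid volume

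*Protocol*

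**What the plan says.** Section 8 has a heading about the intervention, but its text acts on participation. A woman may withdraw from the study, and the investigator may, at his discretion, end her "participation in the study if he believes it necessary for any reason including" six grounds: pregnancy (8.1), "Symptom improvement where surgery is not necessary" (8.2), an adverse event that rules out continuing (8.3), clinically significant laboratory results (8.4), non-compliance (8.5) and persistent side effects (8.6). Neither Section 8 nor any other part of the protocol describes stopping drug while staying under observation, or an early-termination visit.

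Table 1 (Section 3.4) marks laboratory tests and ultrasound at Visit 1 and Visit 4 only. Section 6.4 agrees: blood is taken "pre and post study duration to compare the results at baseline and end of study". Adverse events are reviewed at Visits 2, 3 and 4, at the follow-up visits and by weekly call.

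Section 9 puts the primary analysis at 12 weeks, using a generalized linear model by arm. Tumor size and laboratory values are among its continuous outcomes. A mixed model over entry, week 6 and week 12 is added. Primary outcome measures are not imputed, and the effect of drop-out is to be examined by sensitivity analyses.

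**The concern.** The grounds in Section 8 are not neutral. Three of them (8.3, 8.4, 8.6) describe suspected harm, 8.2 describes benefit, and 8.5 describes poor adherence. If the investigator acts on them as written, the woman leaves the study rather than only stopping the capsules, and her week-12 blood tests and ultrasound are not taken. The 12-week comparison then rests on women selected after randomization for reasons that may be related to treatment. This touches the primary outcome (fibroid size) and the pre-post laboratory comparison in Section 2.3, which includes liver enzymes; Section 3.6 lists liver function abnormalities as a risk of the drug. It also works against outcome completeness, which Section 2.2 makes a feasibility objective.

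**Working it through.** The plan states no figure on this point, so there is none to reproduce. The check sets Section 8 against the schedule and the analysis.

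**1. Scheduled measurements after baseline (Table 1, Sections 3.4 and 6.4)**

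| | Completes Visit 4 | Ended between Visits 3 and 4 | Ended between Visits 2 and 3 |
|---|---|---|---|
| Laboratory tests | 1 | 0 | 0 |
| Ultrasound | 1 | 0 | 0 |
| Visits with adverse event review, to week 12 | 3 | 2 | 1 |
| Weekly calls | about 12 | until exit | until exit |

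No laboratory test is scheduled on treatment before Visit 4. A result that triggers 8.4 before week 12 must therefore come from an unscheduled test. That woman has the unscheduled result but not the week-12 one.

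**2. Can the planned analysis recover the missing values?**

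- *12-week model.* A woman without a week-12 value drops out of it. Imputation of the primary outcome measures is ruled out; multiple imputation is reserved for covariates.
- *Mixed model.* It names week 6, but Table 1 has no week-6 laboratory test or ultrasound. For these two outcomes an early leaver has a baseline value only and says nothing about change. The missing-at-random assumption then conditions on no outcome value observed after randomization.
- *Sensitivity analyses.* They show how far the result depends on assumptions about the missing values. They do not supply the values.
- *Adverse events.* Events recorded before exit still enter the Fisher comparison by arm, so this part of the safety analysis keeps what was seen.

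**3. Weight of one woman**

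- 60 randomized (Synopsis): 60 / 2 = 30 per arm; 1 / 30 = 3.3%.
- 72 randomized (Section 3.2): 72 / 2 = 36 per arm; 1 / 36 = 2.8%.

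**4. How many women?**

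Section 3.2 anticipates 20% withdrawal: 0.20 × 60 = 12, or 0.20 × 72 = 14.4. This is an expected rate for exits of every kind, not a ceiling, and it is not split by reason, time or arm. If, as an assumption, 5% to 30% left before Visit 4, that would be 3 to 18 of 60 or 3.6 to 21.6 of 72. Only an unknown part of these would be ended by the investigator under Section 8.

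**The case against.** The strongest reply is that Section 8 permits removal and does not require it. The investigator can already stop the drug and keep the woman in the study, and 8.3 covers only events that preclude continuing. Section 2.2 also counts retention and adherence separately, so a woman who misses doses is not automatically out. This is right, and a reader who inferred that every woman with side effects must leave would go beyond the text. What stands is that the only action written is to end participation, so continued measurement depends on individual discretion.

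A second reply is that women who leave are not ignored. Section 7 promises immediate care and tells women to call, Section 10 monitors withdrawals related to adverse events, and Section 9 reports drop-out patterns and adds sensitivity analyses. This also stands. It defeats any claim that women removed for harm vanish from the safety data. It does not schedule a blood test or an ultrasound.

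A reader might also infer that women who have no operation go without safety contact after week 12. The protocol foresees such women: at week 12 they are "counselled about the need for surgery if there are significant changes in fibroid size". The follow-up visits are "Scheduled at 2 and 6 weeks post surgery", and Section 3.4 has the nurse "remain in contact with the participant for the 12 week duration weekly to enhance compliance to study medication intake and to record adverse events". But the Synopsis and Section 3.6 promise contact throughout the study, and the Synopsis gives 18-20 weeks in total. The text is therefore ambiguous and does not establish a gap. A completer's whole drug exposure is covered by then in any case. This reading is not part of the finding.

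**Conclusion.** The point holds in limited form. Section 8 writes an exit from the study where a stop of drug would serve. For laboratory values and fibroid volume, an exit before Visit 4 means 0 scheduled post-baseline measurements instead of 1. The planned analysis cannot restore them.

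The size of the effect on the results cannot be given. The number of women removed under Section 8 before week 12 is unknown, and nothing in the protocol shows that removal would differ by arm. The direction of any bias is open too, since the grounds include both harm and benefit. The conclusion assumes that the investigator uses the clause as written and that no early-termination procedure exists outside this protocol. A separate analysis plan would not cure the gap, because it cannot create measurements that were never taken. The trial is not invalidated: completers are well covered to week 12. The change is worth making because the loss is foreseeable and cheap to prevent.

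**What to change.** Rewrite the exit clause itself; an added sentence would leave the present power in place.

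- On grounds 8.1 to 8.6 the investigator may discontinue study drug. Participation ends only if the woman withdraws consent or cannot be followed.
- A woman who stops drug keeps the existing weekly calls and visits, including the Visit 4 laboratory tests and ultrasound at week 12. Her values are analyzed in her randomized arm.
- For pregnancy (8.1), safety follow-up runs to the outcome, and fibroid volume is reported separately.
- If she will not attend Visit 4, safety laboratory tests and an adverse event review are done at stopping. They are reported as such and not as week-12 values.

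The cost is protocol wording, with matching consent text if needed, continued calls and visits for early stoppers, and a 15-20 mL draw at stopping for those who will not attend Visit 4. The comparison will then include some women off drug at week 12, which may dilute a drug effect but keeps the randomized groups intact. A woman whose surgery is brought forward still cannot give a comparable week-12 volume.

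Optionally, the protocol could also state whether weekly contact ends at week 12 or continues to weeks 18-20 for women without surgery. That is a clarification of wording only.

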9. STATISTICAL CONSIDERATIONS

Exploratory data analysis will be used to evaluate variable distributions at study entry. Any unusual, outlying and out-of-range observations will be checked. Missing data patterns, especially due to drop-out, will be evaluated and reported. We will explore the distributions of potentially confounding variables, i.e. any demographic, family and medical history characteristics that are strongly predictive of the study efficacy outcomes. Differences in distributions of these potential confounders will be checked across the study arms as these might occur due to chance despite the randomization, especially for relatively small clinical trials (25). Results of these analyses will be used to refine the analyses and guide model building. The final model will include adjustments for the confounders that are differentially distributed by arm.

For feasibility endpoint, we will report the following proportions: subject retention, outcomes, and adherence to the study regimen, with their 95% exact binomial confidence intervals. Subject satisfaction score will be summarized (using mean and standard deviation) for the overall study sample and by treatment arm. Two-sided t-test will be used to compare subject satisfaction scores between the treatment arms.

Safety endpoint, including adverse events will be tabulated overall and by the study arm. Proportions of events by type across the treatment arms will be compared using Fisher's exact test. To account for multiple comparisons, false discovery rate (FDR) procedure will be used. FDR controls the expected proportion of incorrectly rejected null hypotheses ("false discoveries") at 5%.

Preliminary efficacy endpoint will be reported by treatment arm. Primary analysis will focus on 12-week outcomes. The efficacy outcomes will be compared across the treatment arms using generalized

A double blinded, phase II, randomized controlled trial to study the effects of simvastatin in patients with uterine leiomyoma.

From the subject volume and similar trials at our institution, we expect to be able to complete the trial. We also expect safety of simvastatin in symptomatic leiomyoma subjects to be similar to the general population. We also expect the preliminary efficacy to show symptom improvement and smaller tumors in the simvastatin arm.

10. DATA AND SAFETY MONITORING PLAN

The data will be monitored by verification that informed consent was obtained appropriately prior to any study-specific procedures and documented properly. The following will also be monitored: adherence to protocol eligibility criteria; compliance with protocol procedures; documentation of procedures and assessments related to protocol-required safety assessments; evaluation and documentation of adverse events, especially any serious adverse events or withdrawals related to adverse events; conduct and documentation of study endpoints; procedures for documenting accountability and; appropriate administration of the investigational drugs.

The collection and reporting of adverse events identified in the execution of this clinical study will be described as follows: definitions of adverse events and study period; description of the identification and reporting of on-going adverse events; description and reporting procedure for serious adverse events; procedure for IND Safety Reports and; Procedure for IRB notification and study stopping rules.

The PI will have the sole responsibility for monitoring and oversight of problems / events.

